## 1.4 Sample Size Calculation

Sufficient subjects will be screened so that approximately 198 subjects are randomized (approximately 66 per group) to ensure approximately 180 (approximately 60 per group) evaluable subjects complete the entire study (allowing for 10% for drop-outs post-baseline).

The study will be sufficiently powered to demonstrate statistically significant differences between group Toothpaste/Mouthwash (a toothpaste containing 0.454% w/w SnF2 with a mouthwash containing 0.07% w/w CPC) compared to the Negative Control (a toothpaste containing 0.243% w/w sodium fluoride) for Mean NBS (Overall) at Week 12 (primary objective). CCI

CCI

The dropout rate and SD estimates are based on the review of the sponsor clinical study evaluating 0.454% SnF2 toothpastes. As the estimate was based on only one study, the sample size was inflated from the initial calculation to account for this.

## 2 Planned Analyses

### 2.1 Interim Analysis

No interim analysis is planned.

### 2.2 Final Analyses

The final planned primary analyses will be performed after the completion of the following sequential steps:

1. All subjects have completed the study as defined in the protocol.
2. All required database cleaning activities including any external data reconciliation have been completed and database has been locked.
3. All criteria for unblinding the randomization codes have been met and the randomization codes have been distributed.

## 3 Considerations for Data Analyses and Data Handling Conventions

### 3.1 Baseline Definition

For all endpoints, the baseline value will be the Day 0 (Visit 2) assessment with a non-missing value.

Unless otherwise stated, if baseline data is missing no derivation will be performed and the baseline value will be set to missing.

### **3.2 Subgroups/Stratifications**

Subjects who satisfy the study selection criteria will be stratified by their gender resulting in the following stratum:

- Stratum 1: Sex = Male
- Stratum 2: Sex = Female

### **3.3 Centers Pools**

Since this is a single center study, pooling of centers is not applicable.

### **3.4 Timepoints and Visit Windows**

The timepoints and visits for this study are defined in [Table 1-1](#) “Schedule of Activities”. Any deviation from the study schedule may be reviewed on a case-by-case basis at the Blind Data Review Meeting (BDRM) to determine whether the data should be excluded from the Per Protocol (PP) population.

## **4 Data Analysis**

Data analysis will be performed by **CCI** with oversight from Haleon. The statistical analysis software used will be SAS version 9.4 or higher.

Prior to database closure a BDRM will be conducted in which various aspects of the trial will be discussed and agreed.

Except as described below, all listings will be produced for all randomized subjects.

### **4.1 Populations for Analysis**

#### **4.1.1 Subject Disposition**

Screen failures are defined as subjects who consent to participate in the clinical study but are not subsequently randomized. An enrolled subject is one who has agreed to participate in the clinical study following completion of the informed consent process directly or via their legally authorized representative and successfully met eligibility criteria to proceed beyond the screening visit.

The number of subjects screened, enrolled, and randomized will be presented in Table 14.1.1.

The number and percentage of screen failure subjects (subjects not randomized) with reasons why subjects are not randomized will be displayed. Percentages for screen failure subjects will be based on the total number of subjects screened.

The number and percentage of randomized subjects who complete and discontinue the study, broken down by reason for discontinuation, will be presented by study product and overall, in Table 14.1.1. The percentages will be based on the number of subjects randomized.

Table 14.1.1 will also present the number and percentage of randomized subjects in each of the defined analysis populations (as defined in [Section 4.1.3](#)) by study product and overall. Percentages will be based on the number of subjects randomized.

Subject disposition including demographic data (age, sex, race and ethnicity), screening date, study product start date/time, subject status (completer, Yes/No), study completion or withdrawal date, duration (in days) in the study (defined as [(date of completion or withdrawal – study product start date) + 1], and the primary reason for withdrawal and further details for withdrawal will be listed (Listing 16.2.1.1) by study product.

Subject disposition information will be listed for non-randomized subjects (Listing 16.2.1.2), including demographic information (age, sex race and ethnicity), enrolled (Yes/No), screening date, reason for screen failure and any further details of reason for screen failure.

#### **4.1.2 Protocol Deviations**

Protocol deviations will be tracked by the study team throughout the conduct of the study. Data will be reviewed prior to unblinding and closure of the database to ensure all important deviations are captured and categorized. Subjects with important protocol deviations liable to influence the efficacy outcomes will be excluded from the PP population. Subjects may also be identified as having important protocol deviations not leading to exclusion from the PP population.

Important deviations of the protocol procedures may include, but will not necessarily be limited to the following:

- Consent procedures
- Inclusion or exclusion criteria
- Concomitant medication/therapy
- Study procedures
- Randomization procedures
- Study drug dosing/study product administration/study product compliance
- Visit schedule/interval
- Other

The specific details of the important protocol deviations will be listed in the Protocol Deviation Management Plan, and the assessment process will be specified in the Blind Data Review Plan. Subjects with important protocol deviations will be identified at the BDRM.

The number and percentage of subjects with at least one important protocol deviation, subjects with important protocol deviations not leading to exclusion from PP population with reasons for deviations and subjects with important protocol deviations leading to exclusion from the PP population with reasons for deviations will be presented by study product and overall, for all randomized subjects (Table 14.1.2) and listed in Listing 16.2.2.1.

All protocol deviations collected on the protocol deviation case report form (CRF) will be listed in Listing 16.2.2.2. The listing will present date of deviation, type of deviation and deviation description.

### 4.1.3 Analysis Populations

Five analysis populations are defined.

Population	Definition / Criteria	Analyses Evaluated
Safety	Comprise of all randomized subjects who receive at least one dose of investigational product. Summaries and analyses of this population will be based on the investigational product the subject received.	Demographics Safety
Modified Intent-To-Treat (mITT)	Comprise of all randomized subjects who receive at least one dose of investigational product and complete at least one-post Baseline efficacy assessment. This population will be based on the investigational product the subject was randomized to. All subjects who receive a randomization number will be considered randomized.	Demographics Compliance Efficacy
Per-Protocol (PP)	Comprise of all subjects in the mITT population who have at least one non-missing efficacy assessment considered to be unaffected by protocol deviations.  Protocol deviations that may exclude subjects from the PP population are defined in Section 4.1.2 (Protocol Deviations)	Efficacy
MGI Repeatability	Comprise of all subjects who have at least one repeat MGI clinical assessment at any visit.	Repeatability for MGI
TPI Repeatability	Comprise of all subjects who have at least one repeat TPI clinical assessment at any visit.	Repeatability for TPI

**NOTE:**

Please refer to [Appendix 1](#): List of Data Displays, which details the population to be used for each display being generated.

The number of subjects included in each of the analysis populations will be presented (Table 14.1.1). Subjects excluded from any of the analysis populations will be listed in Listing 16.2.3.1, with the reason for exclusion.

The primary population for assessment of efficacy will be the mITT population. A PP analysis will be performed for the primary endpoint if  $\geq 10\%$  subjects in the mITT population are excluded from the PP population. Efficacy data determined to have been potentially impacted by a protocol deviation will be excluded from the PP analysis. The decisions as to whether or

not a protocol deviation impacts efficacy data and whether to perform a PP analysis will be made during BDR, prior to database lock.

Any repeat clinical data collected for the repeatability assessment will only be used to assess repeatability. The main assessment of efficacy will be based on the initial assessment.

## **4.2 Subject Demographics and Other Baseline Characteristics**

### **4.2.1 Demographic Characteristics**

Descriptive statistics [number of subjects (n), mean, SD, median, minimum and maximum for continuous variables, frequency count (n) and percentage (%) of subjects for categorical variables] will be presented for demographic characteristics by study product and overall. These variables include age (years), sex, race, ethnicity and will be presented for the Safety population (Table 14.1.3.1) and the mITT population (Table 14.1.3.2) and if applicable, for the PP population (Table 14.1.3.3).

Demographic information will be listed for all randomized subjects in Listing 16.2.4.1.

### **4.2.2 General Medical History**

Medical and surgical history (in the last year) including allergies or drug sensitivity will be listed in Listing 16.2.4.2 for all randomized subjects, with start date and end date or ongoing at the start of study product.

## **4.3 Treatments (Study Product, Rescue Medication, other Concomitant Therapies, Compliance)**

Randomization details will be listed, including the randomization number, stratification group, the planned study product, the actual study product the subject was randomized to and the randomization date (Listing 16.1.7.1) for all randomized subjects.

The study product kit allocations will be listed (Listing 16.1.7.2) for all randomized subjects, including kit number and study product information.

### **4.3.1 Study Product Compliance and Exposure**

Compliance data will be summarized for the mITT population.

A table (Table 14.2.1) with frequency count (n) and percentage (%) of subjects for compliance response (Yes/No) will be presented by study product and Time period 'Baseline to Week 6' and 'Week 6 to Week 12'.

Study product compliance (compliance response [Yes/No]) will be listed in Listing 16.2.5.1 for all randomized subjects by study product.

Supervised study product application (subject number, visit, and time of the supervised procedure) will be listed (Listing 16.2.5.2) for all randomized subjects.

### 4.3.2 Prior and Concomitant Medication

Prior medications/treatments, including prescription and non-prescription drugs, dietary supplements and herbal remedies, taken in the last 30 days and prior to signing the informed consent form, will be documented in the CRF. The prior and concomitant medications will be coded using a validated medication dictionary, CCI

CCI

Prior medications and prior non-drug therapies will be listed by subject, with drug name, CCI drug synonym, reason for medication, route, dose, frequency, start date, start day relative to the study product start date, and end date and end day relative to the study product start date (Listing 16.2.4.3) for safety population. Prior medications are defined as those which stopped before the study product start date.

Concomitant medications and concomitant non-drug therapies taken during treatment will be listed similarly (Listing 16.2.4.4) for safety population with either ongoing or end date displayed. Concomitant medications are defined as medications that started or stopped on or after the study product start date or are ongoing.

Unknown dates will not be imputed. However, if the start or stop date is unknown, then it will be assumed to be concomitant medication unless the partial start date or stop date indicates differently.

## 4.4 Analysis of Efficacy

The primary population for assessment of efficacy will be the mITT population. No repeat assessment data is to be used in any efficacy analyses.

Descriptive summary statistics will be presented for both observed values and Change from Baseline at each time point for primary and secondary endpoints.

All p-values presented will be two-sided and assessed at the 5% significance level. A sequential testing strategy will be used to adjust for the comparisons between the Toothpaste/Mouthwash combination and the Negative Control in Overall NBS and Interproximal NBS at each assessment time point.

At each time point, the Interproximal NBS will only be assessed for confirmatory evidence if the Overall NBS achieves a statistically significant greater reduction for the Toothpaste/Mouthwash combination compared to the Negative Control. This strategy will begin at Week 12, and then move to Week 6, only moving to the earlier time point for confirmatory evidence if the 'Week 12' time point achieves statistically significant greater reductions for the Toothpaste/Mouthwash compared to the Negative Control for both Overall NBS and Interproximal NBS. There will be no further adjustments for multiplicity for the other secondary endpoints.

The observed margin (OM) option in SAS will be used when estimating least square means/performing MMRM analysis.

## 4.4.1 Primary Efficacy Endpoint

### 4.4.1.1 Primary Efficacy Endpoint Definition

The primary endpoint of this study is Overall NBS at Week 12.

Gingival bleeding will be assessed according to the EBI, by inserting a periodontal probe into the gingival crevice and sweeping from distal to mesial around the tooth at an approximate angle of 60°, while in contact with the sulcular epithelium. Each of six gingival areas (distobuccal, midbuccal, mesiobuccal, distolingual, midlingual, and mesiolingual) around each tooth will be assessed. All scorable teeth in one quadrant should be probed first (approximately 30 seconds) before recording the number of gingival units which bleed.

The BI/EBI score has a range of 0 to 2 as described in [Table 4-1](#).

**Table 4-1 Bleeding Index Scoring System**

Score	Description
0	No bleeding after 30 seconds
1	Bleeding observed within 30 seconds of probing
2	Bleeding observed immediately on probing
9	Missing tooth or not qualified tooth

The EBI will be assessed by the same examiner on all evaluable teeth from Baseline onwards as indicated in the Schedule of Activities ([Table 1.1](#)).

The Overall NBS score for each subject will be calculated as the number of evaluable tooth sites with an EBI score of either 1 or 2.

Descriptive statistics (n, mean, SD, SE, median, minimum, maximum) of Overall NBS will be provided by study product for the mITT population (Table 14.2.2.1.1).

The raw mean and SE of the Overall NBS will be presented graphically over time for each study product in Figure 14.2.2.1.3 for the mITT population.

Individual data for the NBS will be listed for each subject by study product and visit in Listing 16.2.6.1 for all randomized subjects.

### 4.4.1.2 Statistical Hypothesis, Model and Method of Analysis

The primary hypothesis test will be the comparison between the Toothpaste/Mouthwash and the Negative Control in the mITT population.

The following null and alternative hypotheses will be evaluated:

- H0: There is no difference in the Overall NBS at 12 weeks between the Toothpaste/Mouthwash and Negative Control.

Haleon Confidential

CCI Statistical Analysis Plan Template v7.0

Page 20 of 44

- H1: There is a difference in the Overall NBS at 12 weeks between the Toothpaste/Mouthwash and Negative Control.

A Mixed Model for Repeated Measures (MMRM) will be used, with Overall NBS values as the dependent/response variable, the categorical time point Week 12, treatment group (Toothpaste/Mouthwash and Negative Control) and treatment group by time point interaction as fixed effects and baseline Overall NBS as a covariate. Gender will also be included as stratification factor. Subject will be included as a repeated measure with an unstructured covariance matrix. The Kenward Roger degrees of freedom approach will be applied. If unstructured covariance matrix does not converge, the following covariance structures will be applied in order until convergence is achieved: 1) Toeplitz, 2) compound symmetry (CS).

Using the above model, the least squares differences at Week 12 from the MMRM will be presented, along with the two-sided p-value and 95% CI in Table 14.2.2.2.1. The % adjusted mean difference will also be presented.

The assumption of normality and homogeneity of variance in the MMRM will be investigated. In case of violation of these assumptions, a suitable non-parametric test (van Elteren test adjusting for gender stratification) will be performed for between product comparison to support the MMRM results.

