8.3.1 Primary Endpoint Analysis(es)

The primary endpoint of this study is NBS at Week 12; the primary hypothesis test will be the comparison between the Toothpaste/Mouthwash (a toothpaste containing 0.454% w/w SnF2

Property of Haleon- Confidential

May not be used, divulged, published or otherwise disclosed without the consent of Haleon

CCI

Abbreviated Clinical Protocol Template v1.0

with a mouthwash containing 0.07% w/w CPC) group and the negative control (a toothpaste containing 0.243% w/w NaF) group in the mITT population.

The NBS (overall) for each subject at each visit is calculated as the number of evaluable tooth sites with a BI score of either 1 or 2.

NBS (overall) at Week 12 will be analysed using a Mixed Model with Repeated Measures (MMRM) with investigational product, visit and [investigational product x visit] interaction as fixed effects, and Baseline NBS as a covariate. Subject will be included as a repeated measure with unstructured covariance matrix. Kenward Rogers degrees of freedom approach will be applied (Kenward, 1997). The least squares differences at Week 12 from the MMRM will be presented, along with the two-sided p-value and 95% CIs.

The assumptions of normality and homogeneity of variance in the MMRM will be investigated. In case of violation of these assumptions, a suitable non-parametric test (adjusted for the randomization stratification) will be performed and the results will be provided to support the MMRM results.

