#### **4.4.4 Handling of Missing Values/Censoring/Discontinuations**

For the primary analyses, missing data will not be replaced or imputed. Subjects who withdraw from the study prematurely will be included in the statistical analyses up to the point of discontinuation. Subjects who withdraw will not be replaced. In the event that a subject has no individual BI, MGI or TPI assessments available at a given visit, the Mean NBS, BI score, MGI score or TPI score will also be considered as missing for that visit.

MMRM analyses account for missing data using ‘a missing at random’ assumption, i.e., there is a systematic relationship between the propensity for missing values and the observed data, but not the missing data. Under such assumptions, MMRM is shown to provide unbiased estimates of the treatment effect whilst analysis of only complete cases using analysis of covariance (ANCOVA) is biased (Ashbeck, 2016; Baron, 2008).

Such complete case analysis requires a ‘missing completely at random’ assumption to remain unbiased and this is unlikely to hold, i.e., the fact that the data are missing is independent of the observed and unobserved data. Using an MMRM, it will therefore be assumed that a subject with missing data at one post- Baseline assessment visit would have obtained a similar efficacy result at that visit compared to a subject using the same investigational product with similar non-missing results at other timepoints (Baseline and the other post-Baseline assessment visits).

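### SAP 4.4.1.2 writes the primary MMRM with Week 12 as its only time point and two of the three arms, contradicting the protocol and the rest of the SAP

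*SAP*

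**What the plan says.** SAP 4.4.1.2 is the only place in the SAP that sets out the terms of the primary model. It lists "the categorical time point Week 12, treatment group (Toothpaste/Mouthwash and Negative Control) and treatment group by time point interaction as fixed effects", with baseline Overall NBS as covariate and sex added as the stratification factor. The same paragraph continues: "Subject will be included as a repeated measure with an unstructured covariance matrix". It gives Toeplitz and then compound symmetry as fallbacks.

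Protocol 8.3.1 describes the model differently: "with investigational product, visit and [investigational product x visit] interaction as fixed effects, and Baseline NBS as a covariate". It restricts neither the visits nor the arms, and it has no sex term.

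SAP 4.4.2 and 4.4.3 reuse this model for Week 6 and Week 12, for Reference Toothpaste against Negative Control, and for Toothpaste/Mouthwash against Reference Toothpaste. All three overall-NBS comparisons go to Table 14.2.2.2.1, and Appendix 1 lists one raw model output for that table.

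SAP 4.4.4 defends the MMRM on the ground that, when data are missing at random, "analysis of only complete cases using analysis of covariance (ANCOVA) is biased". It assumes that a subject with a missing visit would have resembled a subject on the same product "with similar non-missing results at other timepoints (Baseline and the other post-Baseline assessment visits".

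Table 5-1 lists three changes from the protocol: the recommendation question, and the recording of oral soft tissue and of oral hard tissue findings. None concerns visits, arms or the sex term.

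**The concern.** The Week 12 comparison of Toothpaste/Mouthwash with Negative Control alone decides whether the study succeeds. A programmer who follows SAP 4.4.1.2 would fit one record per subject. One who follows the protocol would fit two. These are different analyses, and only the second can use Week 6 data from a subject who has no Week 12 visit. Such subjects belong to the mITT population, which needs only one post-baseline assessment. The missing-data argument in SAP 4.4.4 depends on their contributing.

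The model as written also cannot deliver what later sections ask of it: it has no Week 6 level and no Reference Toothpaste arm. Because every secondary and exploratory endpoint refers back to it, the ambiguity spreads to all of them.

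**Working it through.** **The plan's own figure.** 60 evaluable per group with 10% added gives 60 × 1.10 = 66 per group and 3 × 66 = 198, as stated. Dividing instead gives 60 / 0.90 = 66.7, so 67 per group and 201 in total; the plan says approximately, so this is immaterial. The power calculation cannot be reproduced because effect, SD and power are redacted. Nothing below depends on it.

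**Does one time level reduce the model to ANCOVA?** The columns are intercept, arm, time, arm × time, baseline and sex: six. With one time level, time equals the intercept and arm × time equals arm, so the rank is 4. On a test data set the Week 12 contrast was −0.63123 from this model and −0.63123 from complete-case ANCOVA. With one record per subject, unstructured, Toeplitz and compound symmetry are all the same single variance. The collapse is exact, and the number of arms plays no part in it.

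**How many subjects are affected?** Those with Week 6 but not Week 12 number at most 0.10 × 66 = 6.6 per arm. Anyone who leaves before Week 6 is outside mITT and is not recovered by either model. If 5% leave after Week 6 the number is 3.3 per arm; if 3%, 2.0.

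**How large is the bias?** Assumed values, none from the documents: 66 per arm, residual SD 1, true Week 12 effect −0.6 SD, Week 6/Week 12 residual correlation 0.3 to 0.8, and a logistic dropout slope of 1.5 per SD of Week 6 bleeding. There were 1,500 runs per scenario (Monte Carlo error about 0.005 SD). Bias of the Week-12-only estimate in SD units, with the full 10% lost after Week 6:

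| Correlation | Same pattern in both arms | Control arm only | Opposite directions |
|---|---|---|---|
| 0.3 | −0.003 | 0.039 | 0.076 |
| 0.6 | −0.002 | 0.063 | 0.144 |
| 0.8 | 0.016 | 0.089 | 0.193 |

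The two-visit model stayed within 0.02 SD of the truth in every cell. The standard error of the Week-12-only estimate was about 0.19 SD, so the non-zero biases run from about 0.2 of a standard error (0.039 / 0.186) to about one (0.193 / 0.190). With the same dropout pattern in both arms the cost is precision only: standard errors of 0.185, 0.192 and 0.183 against 0.183, 0.185 and 0.175, or about 1 to 5%.

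A second run, with an assumed SD of 10 sites and correlations of 0.5 to 0.7, looked at smaller post-Week-6 losses:

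- 3%: 0.13 to 0.17 sites (control only) and 0.3 to 0.4 sites (opposite), or 0.01 to 0.04 SD after dividing by 10.
- 5%: 0.3 to 0.4 and 0.45 to 0.67 sites, or 0.03 to 0.07 SD.
- Same pattern in both arms: about 0.

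Repeating these two rates with the first simulation's set-up and the same correlations gave 0.02 to 0.06 SD and 0.03 to 0.09 SD. They are orders of magnitude, not estimates.

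Positive bias against a negative effect means attenuation, so these scenarios work against the test product. Swapping the arms' roles reverses the sign.

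**What does the two-arm restriction cost?** Residual degrees of freedom are about 120 − 4 = 116 with two arms and 180 − 5 = 175 with three. The t critical values are 1.981 and 1.974, a ratio of 1.0036, so under 0.4%. The third arm also drops out of the variance estimate.

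**The case against.** The strongest reply is that the sentence is drafting shorthand which names the primary time point and contrast. The paragraph calls the model a repeated-measures model, gives it an interaction and three covariance structures, and takes the Week 12 difference from it; none of this has a purpose with one visit. Later sections apply the same model to Week 6 and to the Reference Toothpaste, one raw output serves all overall-NBS comparisons, and the silence of Table 5-1 fits no change being intended. This stands. A reader might infer that the sponsor has settled on a complete-case ANCOVA; the documents do not support that.

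A reader might also infer that leaving out an arm helps cause the collapse, or that the primary result will be biased. Neither follows. The collapse comes from the single time level alone. Nothing in the documents suggests that dropout depends on Week 6 bleeding differently by arm, and Protocol 9.8 asks subjects who stop product to stay for the remaining assessments. Nor does the protocol say in terms that all three arms enter one model; that is the natural reading of its product term.

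Different adjusted means for one arm within one table would arise only from separate pairwise fits. The SAP's references to two products may merely describe the display.

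What the reply does not remove is the contradiction. Intent has to be reconstructed from other sections, while the one sentence that states the terms says something else.

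**Conclusion.** The point holds as an inconsistent specification of the primary model, not as a settled switch of method. If the sentence is followed literally, the analysis is a Week 12 complete-case ANCOVA adjusted for baseline and sex, the approach that SAP 4.4.4 rejects, and Week-6-only subjects are lost from the primary estimate.

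The harm is conditional. It is about zero under random dropout or a pattern common to both arms. With arm-dependent dropout driven by Week 6 bleeding, it is roughly 0.01 to 0.04 SD, 0.03 to 0.07 SD and 0.04 to 0.19 SD at 3%, 5% and 10% loss after Week 6. The 10% case treats all planned dropout as occurring after Week 6 and being of this kind, so it is an upper case for the planned rate under these assumptions. The two-arm wording is a minor efficiency and consistency matter. The specification should still be settled before unblinding, because it governs the only test that decides success and is carried into every other efficacy comparison.

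**What to change.** In SAP 4.4.1.2, specify:

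- one MMRM on Overall NBS at Weeks 6 and 12, with all three products;
- fixed effects for product, visit, product × visit and sex, with Baseline Overall NBS as covariate;
- unstructured covariance and Kenward-Roger degrees of freedom;
- Toothpaste/Mouthwash minus Negative Control at Week 12 as the primary contrast, with the other contrasts and Week 6 taken from the same fit.

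Use the same form, with the matching baseline, for every secondary and exploratory endpoint. Add the sex term to Table 5-1, since it is not among the protocol's model terms. If a Week-12-only or two-arm model is really intended, declare it in Table 5-1 and rewrite SAP 4.4.4, whose argument would no longer apply.

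The cost is SAP wording before unblinding. No data collection, visit or sample size changes.

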**Reference Toothpaste versus Negative Control:**

- Baseline Overall NBS for Overall NBS at Week 6 and Week 12; Baseline Interproximal NBS for Interproximal NBS at Week 6 and Week 12.
- Baseline Mean Overall EBI for Mean Overall EBI at Week 6 and Week 12; Baseline Mean Interproximal EBI for Mean Interproximal EBI at Week 6 and Week 12.
- Baseline Mean Overall MGI for Mean Overall MGI at Week 6 and Week 12; Baseline Mean Interproximal MGI for Mean Interproximal MGI at Week 6 and Week 12.
- Baseline Mean Overall TPI for Mean Overall TPI at Week 6 and Week 12; Baseline Mean Interproximal TPI for Mean Interproximal TPI at Week 6 and Week 12.

Adjusted mean product differences will be provided, along with 95% CIs.

The assumption of residual normality and variance homogeneity in the MMRM analysis used to analyze secondary endpoints will be investigated through residual plots. If violated, data transformation or a nonparametric method (van Elteren test adjusting for gender stratification) will be used and the results will be provided to support the MMRM results.

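### The nonparametric fallback for the primary endpoint adjusts for sex but drops baseline NBS; a sex-stratified rank-ANCOVA would keep it at almost no cost

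*SAP*

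**What the plan says.** SAP 4.4.1.2 defines the primary MMRM for Overall NBS with "baseline Overall NBS as a covariate" and with sex as the stratification factor. If the checks of normality and homogeneity of variance fail, "a suitable non-parametric test (van Elteren test adjusting for gender stratification) will be performed for between product comparison to support the MMRM results".

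For the secondary endpoints, SAP 4.4.2 gives two options when the residual checks fail: a data transformation, or "a nonparametric method (van Elteren test adjusting for gender stratification) will be used". The primary section does not offer the transformation.

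Protocol 8.3.1 is less specific: "a suitable non-parametric test (adjusted for the randomization stratification) will be performed". It does not name van Elteren, and it does not rule out a baseline covariate.

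Neither SAP section says whether the rank test is applied to the visit value or to change from baseline. The visit value is the natural reading, because the hypotheses in SAP 4.4.1.2 are stated for NBS at Week 12. SAP 4.4 does, however, have both quantities summarized.

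**The concern.** The fallback exists to back up the MMRM when its assumptions are in doubt, which is when a reader will look at it. As written, it adjusts for less than the model it supports. Baseline NBS is measured on every randomized subject, and the sponsor chose it as a model covariate. The van Elteren test uses sex strata alone.

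If baseline predicts Week 12 NBS, leaving it out adds noise. The supporting test can then miss significance beside a correct positive MMRM result. A chance baseline imbalance would also be adjusted for in one analysis and not in the other. What is at stake is how useful and readable the supporting analysis is. The validity of the primary result is not in question.

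**Working it through.** **Inputs from the documents.** Two-sided 5% level: "All p-values presented will be two-sided and assessed at the 5% significance level" (SAP 4.4). Sample size: "approximately 198 subjects are randomized (approximately 66 per group) to ensure approximately 180 (approximately 60 per group) evaluable subjects complete the entire study" (SAP 1.4). The planned dropout rate, from the same section, is 10%. Power, effect size and SD are redacted.

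**The plan's own figure.** 60 × 1.10 = 66 per arm and 3 × 66 = 198, as stated. Dividing by the retention rate instead gives 180 / 0.90 = 200, which is close enough. The plan gives no power for the fallback, so there is nothing further to reproduce.

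**Assumptions.** The correlation ρ between baseline and Week 12 NBS is not given; I used 0 to 0.7. The effect d (in SD units) is set so that the baseline-adjusted parametric analysis has 90% power at 60 per arm.

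**Step 1, formula check with normal errors.**
- d = (1.960 + 1.282) × √(1 − ρ²) × √(2/60). At ρ = 0.5 this is 3.242 × 0.866 × 0.1826 = 0.513.
- A rank test on raw Week 12 values has SD 1 and an effective size of 60 × 3/π = 57.3 per arm. Its power is Φ(d / √(2/57.3) − 1.960). At ρ = 0.5 this is Φ(2.744 − 1.960) = 78%.
- Its efficiency relative to the adjusted model is (3/π)(1 − ρ²): 0.95, 0.87, 0.72 and 0.49 at ρ = 0, 0.3, 0.5 and 0.7. The power is 89%, 86%, 78% and 62%.
- If change from baseline were ranked instead (equal SDs assumed), the power would be 61%, 72%, 78% and 83%. The unstated choice of response therefore matters too.

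**Step 2, simulation.** 4,000 trials per setting, 60 per arm, two sex strata, uniform baseline to mimic the eligibility window, complete data. ANCOVA with baseline and sex stands in for the Week 12 MMRM contrast. Power in %; the last column is rank-ANCOVA minus van Elteren.

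| Errors | ρ | ANCOVA | van Elteren, raw Week 12 | Rank-ANCOVA | Gain |
|---|---|---|---|---|---|
| Normal | 0 | 88.6 | 87.3 | 87.2 | −0.1 |
| Normal | 0.3 | 89.4 | 84.2 | 87.1 | 2.9 |
| Normal | 0.5 | 89.0 | 76.4 | 86.1 | 9.7 |
| Normal | 0.7 | 88.7 | 60.1 | 84.7 | 24.6 |
| Log-normal | 0 | 88.6 | 99.8 | 99.9 | 0.1 |
| Log-normal | 0.3 | 89.1 | 99.1 | 99.8 | 0.7 |
| Log-normal | 0.5 | 88.4 | 92.2 | 99.8 | 7.6 |
| Log-normal | 0.7 | 89.0 | 68.5 | 99.7 | 31.2 |
| t, 4 df | 0 | 88.7 | 96.1 | 96.0 | −0.1 |
| t, 4 df | 0.3 | 89.7 | 92.8 | 96.0 | 3.2 |
| t, 4 df | 0.5 | 89.2 | 83.9 | 94.9 | 11.0 |
| t, 4 df | 0.7 | 88.8 | 64.1 | 94.7 | 30.6 |

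**Step 3, cross-check on skewed counts at 60 per arm.** With log-normal rounded counts and a log-scale effect of 0.25 (NBS about 22% lower), van Elteren against rank-ANCOVA was 67/67/66% against 70/77/89% at ρ = 0.3/0.5/0.7. The gains are 3, 10 and 23 points. A further run with log-SD 0.57 gave 63/64/64/61% against 62/67/75/87% at ρ = 0/0.3/0.5/0.7. The gains are −1, 3, 11 and 26 points.

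**Step 4, type I error.** Rank-ANCOVA rejected in 4.6% to 5.6% of null trials across the skewed-count runs. At ρ = 0.5 with normal errors it rejected in 5.7%, against 5.8% for parametric ANCOVA and 5.5% for van Elteren in the same run. The simulation standard error there is √(0.05 × 0.95 / 4000) = 0.3 points, and parametric ANCOVA is exact in that setting, so I see no sign of inflation specific to rank-ANCOVA.

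**Limits.** Unequal variances, one of the two triggers, were not simulated. The Step 2 rank-ANCOVA ranked both sexes together, then applied van Elteren by sex to the residuals. The simulated data had no sex effect, so I expect ranking within sex, as proposed below, to differ little.

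**The case against.** The strongest case against is that nothing hangs on this test. It runs only if assumptions fail, and both documents give it a supporting role. The success criterion (Protocol 2; SAP 1.2) and the sequential strategy (SAP 4.4) set no condition on it. Van Elteren is a conventional, valid test under sex-stratified randomization, and the MMRM already adjusts for baseline. All of this stands, and it keeps the point minor.

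A reader might go further and infer that the fallback is much weaker than the primary model. The documents do not support that. They give no correlation. The window of 10% to 30% bleeding sites and the full prophylaxis after baseline scoring (Protocol 3 and 4.2) would tend to lower it. NBS is a count, though, and the number of evaluable teeth largely carries over to Week 12, which pulls modestly the other way. Nor does the comparison with the parametric model always favor the model. With log-normal errors, van Elteren beat ANCOVA at 0.3 (99% against 89%) and at 0.5 (92% against 88%), and lost clearly only at 0.7. With rounded log-normal counts (log effect 0.25, log-SD 0.57) the two tied at 0.3 (63% each), and van Elteren trailed 63% to 72% at 0.5 and 63% to 84% at 0.7. The comparison that bears on the proposal is with a rank test that keeps baseline.

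Two other inferences also go too far. The documents contain no data showing that bleeding counts are skewed, so how likely the fallback is to be used is unknown. And Protocol 8.3.1 is not itself at fault, since a sex-stratified rank-ANCOVA would satisfy it. For the secondary endpoints, the transformation option can already keep the MMRM with its baseline covariate.

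**Conclusion.** The point holds as a minor, near-free improvement. The SAP's rank test omits a covariate that the primary model uses and leaves the ranked response unstated. Against a baseline-adjusted rank test at 60 per arm, the power given up is no more than about 4 points at correlations up to 0.3, about 8 to 11 points at 0.5, and about 25 to 31 points at 0.7 (23 in one skewed-count run). These figures rest on assumed correlations, effect sizes and error shapes, on complete data and on equal variances. The unknown correlation governs the size of the gain. In no setting examined was rank-ANCOVA worse by more than about one point, which is within simulation error.

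It does not follow that the primary analysis is biased, that its type I error is wrong, or that the fallback could overturn the trial's conclusion.

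**What to change.** In SAP 4.4.1.2 and 4.4.2, replace the van Elteren test with a sex-stratified rank-ANCOVA for each pairwise comparison:

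1. Within each sex, among the two arms compared, rank the visit value (Week 12 or Week 6) and the endpoint's own baseline.
2. Within each sex, regress the response ranks on the baseline ranks.
3. Apply the sex-stratified mean-score (Cochran-Mantel-Haenszel) test to the residuals.

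This names the ranked response and brings baseline back in. Keep the transformation option in SAP 4.4.2. A short clause confirming that the MMRM decides success whatever the supporting test shows would help readers if the two disagree.

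The cost is one sentence in each section and a few lines of SAS, with no new data and no change to sample size. Protocol 8.3.1 needs no amendment. The change should be made before unblinding. It does not alter the fact that a single-visit rank test uses only subjects observed at that visit, which is equally true of van Elteren.
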